#### Confidentiality Statement

---

The confidential information in this document is provided to you as an investigator or consultant for review by you, your staff, and the applicable Institutional Review Board. Your acceptance of this document constitutes agreement that you will not disclose the information contained herein to others without written authorization from the sponsor.

- **Health Resource Utilization Questionnaire – RUI – (Resource Use Inventory)**- Patient self-reported questionnaire designed to assess health related services the patient has used during the course of the study.
- **Vital signs** – An electrocardiogram will be performed at screening to ensure the subject is healthy enough to participate in the study and does not demonstrate any cardiovascular problems. Blood pressure, heart rate and respirations will be recorded before and after each Renew™ NCP-5 treatment and at every visit.
- **Radiographic and imaging assessments** – Magnetic resonance imaging (MRI) will be performed to rule out other brain pathology including evidence of infection, infarction (including multiple lacunas in a critical memory structure), or other focal lesions. If a history of cerebral aneurysm is suspected, the subject will be referred to their primary physician and/or neurologist. Central Reading of the MRI's will be conducted at MGH. In addition, MRI will be performed at screening and at 12 weeks, 24 weeks and 12 months to assess hippocampal volume and regional cerebral blood flow changes over time. Freesurfer software will be used to measure volume (Schmidt, Storrs, et al., 2018). Studies show that Hippocampal atrophy associated with episodic memory declines over time as observed for word fluency, fluid IQ (block design) and processing speed. These changes are significant in subjects 65-80 years old and noted in 55- 60-year-old subjects (Gorbach, Pudas, et al., 2016).

At select sites, MRI will be used to assess global cerebral blood flow and white matter hyperintensities (WMH) at initial screening, 24 weeks, and 12 months. WMH reflects cerebral hypoperfusion and small vessel disease and is a covariate for vascular disease. WMH lesions are tied to disease progression and decreased cerebral blood flow.

At select sites, Doppler ultrasound will be performed to assess Pulse Wave velocity, flow mediated dilation, endothelial function, and arterial stiffness. KU uses the Moor imaging product to monitor deep tissue oxygenation including SO2, deoxygenated hemoglobin, and oxygenated hemoglobin.

Central reading of all MRI images will be performed at MGH, based on an imaging protocol which will be provided as a separate document. They propose the use of a Siemens Skyra as the platform for imaging to ensure reproducibility and comparability and have developed an automated protocol to ensure standardization across sites. If other platforms are used, MGH will adapt the protocol for their use. It is imperative that, at the very least, the subject's imaging will be performed on the same machine.

---

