### 5.2.3 Payor-based endpoints

The payor-based endpoints, described below, will be used to assess the clinical and cost effectiveness of the Renew™ NCP-5 external counter-pulsation (ECP) for patients with Mild Cognitive Impairment due to Alzheimer’s Disease or Mild Dementia of the Alzheimer’s Type. Effectiveness of ECP on cognitive impairment, compared to active sham group, measured by the clinical effectiveness endpoints identified, will be key in communicating the value and benefits of adding ECP as a treatment option for this patient population. In order for physicians to widely access ECP as a treatment option for their patients, reimbursement from commercial payers will be required. To facilitate reimbursement, the study is measuring the impact of ECP on health related quality of life (HRQoL), reduction in disease burden, and health resource utilization (HRU) to help assess the cost effectiveness of ECP, and potential cost savings for health systems and payers. Results from this study will be presented to Centers for Medicare and Medicaid Services (CMS) and commercial insurers to initiate reimbursement approval of ECP.

- A comparative analysis between treatment and active sham groups on **Health Resource Utilization (HRU) data** will be conducted using the following analysis and time points:
  - The difference in change from baseline analyzed at:
    - 24 weeks
    - 9 months
    - 12 months
  - An average of 24 weeks, 9 months, and 12 months

---

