#### Confidentiality Statement

---

The confidential information in this document is provided to you as an investigator or consultant for review by you, your staff, and the applicable Institutional Review Board. Your acceptance of this document constitutes agreement that you will not disclose the information contained herein to others without written authorization from the sponsor.

- A comparative analysis between treatment and active sham groups in their change of ability to drive based on a self-rated answer to a question
- A comparative analysis between treatment and active sham groups in **vADAS Cog Scores** will be conducted using the following analysis and time points:
  - The difference in change from baseline analyzed at:
    - 24 weeks,
    - 9 months,
    - 12 months;
  - An average of 24 weeks, 9 months, and 12 months
- A comparative analysis between treatment and active sham groups in **ADCS-ADL Scores** will be conducted using the following analysis and time points:
  - The difference in change from baseline analyzed at:
    - 24 weeks
    - 9 months
    - 12 months
  - An average of 24 weeks, 9 months, and 12 months
- A comparative analysis between treatment and active sham groups in **Fall Risk Assessment/Functional Reach Test/TUG Test Scores** will be conducted using the following analysis and time points:
  - The difference in change from baseline analyzed at:
    - 24 weeks
    - 9 months
    - 12 months
  - An average of 24 weeks, 9 months, and 12 months
- A comparative analysis between treatment and active sham groups in **NPI Aggression Index Scores** will be conducted using the following analysis and time points:
  - The difference in change from baseline analyzed at:
    - 24 weeks
    - 9 months
    - 12 months
  - An average of 24 weeks, 9 months, and 12 months
- The answers to the **QOL/Patient Survey** at 12 months after initiation of treatment.

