## 6. STUDY ENROLLMENT AND WITHDRAWAL

### 6.1 Inclusion Criteria

Subjects will meet all inclusion criteria and none of the exclusion criterion. The study is open to both genders and members of all minority groups. Subjects enrolled into the study will:

1. Be 55-85 years of age at the time of signing the informed consent
2. Be able to provide consent or have legally authorized representative/caregiver who can provide consent
3. Be able to read and write in English or Spanish
4. Have a clinical diagnosis consistent with 2011 NIA-AA “core clinical criteria” guidelines for: (i) The diagnosis of dementia due to Alzheimer’s disease or (ii) The diagnosis of mild cognitive impairment due to Alzheimer’s disease:
  - MOCA score of greater than or equal to 11
  - All required checkboxes within the study checklist for “The diagnosis of probable AD dementia” must be “yes” or

---

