#### Confidentiality Statement

---

The confidential information in this document is provided to you as an investigator or consultant for review by you, your staff, and the applicable Institutional Review Board. Your acceptance of this document constitutes agreement that you will not disclose the information contained herein to others without written authorization from the sponsor.

- All required checkboxes within the study checklist for “The diagnosis of mild cognitive impairment due to Alzheimer’s disease” must be “yes”
5. Stable medications for past 30 days and plan to remain on stable medications for the first 24 weeks of study participation for treatment of chronic conditions
  6. Subject should have a caregiver, study partner or companion (which can be a domestic party) who can complete the study assessments. The assessments may be conducted over the phone if they don’t accompany the participant
  7. Must have the potential to improve by at least 2 points or more in the vADAS-COG

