  - **vADAS-Cog** – The vADAS-Cog is made up of ADAS-Cog14 plus three additional tests: the symbol digit test (the number of correct responses in 90 s); the digit span backward test (the number of digits recalled backwards); and the verbal fluency test (animal category in one min). The ADAS-Cog is an instrument devised to assess the severity of cognitive impairment in patients with AD. The scale includes short neuropsychological tests in which the patient performs simple tasks such as word recall, word recognition, and constructional praxis. The cognitive section of the ADAS consists of 11 items, which assess

---

Confidentiality Statement

---

The confidential information in this document is provided to you as an investigator or consultant for review by you, your staff, and the applicable Institutional Review Board. Your acceptance of this document constitutes agreement that you will not disclose the information contained herein to others without written authorization from the sponsor.

the following: language (aphasia), and motor skills (praxis). Rosen, Mohs, et al. (1984) evaluated the test-retest and interrater reliabilities of the individual scale items and the entire scale in patients with dementia of the Alzheimer's type. The ADAS was shown to be valid in the ability to detect patients with clinically diagnosed AD from matched non-demented controls. Because both of the above cognitive and non-cognitive parameters are assessed, the ADAS is a reliable instrument for use in psychopharmacologic trials involving patients with AD.

- **ADCS-CGIC** – assesses clinic global impression of change over time by patient/caregivers and clinicians as indicators of meaningful change and reflects observable changes. Subject should have a caregiver, study partner or companion (which can be a domestic party) and may conduct the assessment over the phone if they do not accompany the participant).
- **ADCS-ADL** – The ADCS-ADL is a set of informant-based items describing performance of activities of daily living assesses the subjects ability to eat, walk, bathe, groom, dress, and other activities of daily living independently by patients with AD. Questions are asked of the caregiver and are given in the form of an interview. Subject should have a caregiver, study partner or companion (which can be a domestic party) and may conduct the assessment over the phone if they do not accompany the participant).

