- **Trail Making TEST A & B** – Neuropsychological test of visual attention and task switching that assesses visual search speed, scanning, speed of processing, mental flexibility, and executive functioning. It is the most commonly used test in clinical practice to evaluate patients for MCI or mild AD.
- **2011 NIA-AA criteria** – In 2011, the National Institute on Aging (NIA) at National Institutes of Health (NIH) and the Alzheimer's Association published revised guidelines (NIA-AA) for modernization of the diagnosis of Alzheimer's disease. In these guidelines, the workgroups identified Alzheimer's disease as a continuum with three distinct stages: Preclinical, Mild Cognitive Impairment and Dementia. Checklists to assist in standardizing assessments across sites used to differentiate MCI and dementia will be implemented in this study.
- **Neuropsychiatric Inventory (NPI)** – A behavioral assessment used to assess dementia-related behavioral problems. The NPI is administered to caregivers of dementia patients. Screening questions are used to assess sub-domains of behavioral functioning such as, but not limited to, agitation/aggression, dysphoria, anxiety, irritability/lability, and appetite and eating abnormalities. Positive responses to these screening questions identify problems in the

---

Confidentiality Statement

---

The confidential information in this document is provided to you as an investigator or consultant for review by you, your staff, and the applicable Institutional Review Board. Your acceptance of this document constitutes agreement that you will not disclose the information contained herein to others without written authorization from the sponsor.

associated sub-domain. The caregiver is then asked to rate frequency, severity, and distress of symptoms in the related sub-domain. Higher scores are correlated to patients with dementia.

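### Health resource use is taken from patient self-report in subjects with MCI or mild AD dementia, although a caregiver is already interviewed at every visit where it is collected

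*Protocol*

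**What the plan says.** **Use of the data.** Section 5.2.3 measures "health resource utilization (HRU) to help assess the cost effectiveness of ECP, and potential cost savings for health systems and payers". It compares the arms on change from baseline at 24 weeks, 9 months and 12 months, and on the average of the three. The study results are to go to CMS and commercial insurers.

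**Informant.** Section 8.1 describes the RUI as a "Patient self-reported questionnaire designed to assess health related services the patient has used during the course of the study". No text shown has the study partner complete or verify it, or checks it against records or claims.

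**Population.** Section 6.1 admits MCI due to AD and AD dementia with a "MOCA score of greater than or equal to 11". Subjects must "Be able to provide consent or have legally authorized representative/caregiver who can provide consent", so some may be enrolled on a proxy's consent.

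**Other informant.** Inclusion criterion 6 reads: "Subject should have a caregiver, study partner or companion (which can be a domestic party) who can complete the study assessments". The partner may answer by phone. For the ADCS-ADL, section 8.1 says: "Questions are asked of the caregiver and are given in the form of an interview". For the NPI it says: "The NPI is administered to caregivers of dementia patients".

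**Driving.** A separate payor item in 5.2.3 compares the arms on "change of ability to drive based on a self-rated answer to a question".

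**The concern.** The RUI asks people whose diagnosis involves memory impairment to report services used over a period of months. What it records is the part of true use that the subject remembers. If both arms forget equally, a real saving appears smaller in absolute terms.

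The error may also differ by arm, because the treatment is meant to improve cognition. If it does, treated subjects report more of their true use than sham subjects do. Randomization and blinding of the subject do not remove this, since the difference arises after baseline through the effect under test. Taking change from baseline does not remove it either. At stake is the cost comparison intended for payers: a real saving could be understated or hidden.

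**Working it through.** The protocol gives no figure for HRU (no rate, variance, recall share or look-back period), so there is nothing of its own to reproduce. The check is of the documents, followed by an illustration on assumed values.

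**1. Visits (Table 2, confirmed by the week 12 list in 8.4.7).**
- RUI: baseline, weeks 12 and 24, months 9 and 12 (5 visits).
- ADCS-ADL and NPI: the same five, plus weeks 6 and 18.
- Overlap: 5 of 5 RUI visits already carry both caregiver-informed instruments.

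**2. Spacing of follow-up RUI visits (Days 84, 168, 252, 365).** 168 − 84 = 84 days; 252 − 168 = 84 days; 365 − 252 = 113 days. This is visit spacing. It equals the recall window only if each RUI covers the time since the last one, which the protocol does not say.

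**3. Scope: the seven payor items in 5.2.3.**

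| Item | Source |
|---|---|
| HRU (RUI) | Subject's recall |
| Driving | Subject's self-rating |
| vADAS-Cog | Performance test |
| ADCS-ADL | Caregiver |
| Fall risk / Functional Reach / TUG | Performance tests |
| NPI aggression | Caregiver |
| QOL/Patient Survey | Appears to be the subject |

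Four of the seven do not use self-report. The recall argument reaches HRU only.

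**4. Spurious difference with no true effect.** Let both arms truly use U services and report shares r_S (sham) and r_T (treated). With the same expected baseline report B in both arms, the difference in change is (r_T·U − B) − (r_S·U − B) = (r_T − r_S)·U, so the baseline term drops out. Relative to the sham report, the excess is (r_T − r_S)/r_S. All shares are assumed:
- 85% vs 90%: 0.05/0.85 = 6%
- 70% vs 75%: 0.05/0.70 = 7%
- 70% vs 80%: 0.10/0.70 = 14%
- 60% vs 70%: 0.10/0.60 = 17%
- 60% vs 75%: 0.15/0.60 = 25%

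**5. A true saving.** Assume a mean of 2 uses per sham subject and a true ratio of 0.80, so a true difference of 2 − 1.6 = 0.40. Take 125 per arm (the maximum of 250, allocated 1:1), variance = 2 × mean and a two-sided 5% z-test. With reported means a and b, SE = √(2(a + b)/125) and power = Φ((a − b)/SE − 1.96).

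| Recall sham / treated | a | b | a − b | b/a | Power |
|---|---|---|---|---|---|
| 100% / 100% | 2.00 | 1.60 | 0.40 | 0.80 | 38% |
| 80% / 80% | 1.60 | 1.28 | 0.32 | 0.80 | 32% |
| 60% / 60% | 1.20 | 0.96 | 0.24 | 0.80 | 25% |
| 70% / 80% | 1.40 | 1.28 | 0.12 | 0.91 | 8% |
| 60% / 75% | 1.20 | 1.20 | 0.00 | 1.00 | 2% |

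Equal under-recall shrinks the absolute difference and leaves the ratio alone. Unequal recall moves both.

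**The case against.** **The instrument is not visible.** Only the heading of Appendix C (HRU) is shown. It may set a look-back period or allow a proxy, and criterion 6 speaks of the partner completing study assessments in general. This stands as a limit on what can be known, but section 8.1 as written says patient self-report. An appendix that allowed a proxy would conflict with it.

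**The arm-differential bias is conditional.** It arises only if treatment changes memory. If memory improves, it runs against the device. This stands. A reader might infer that self-report could manufacture a false saving for the device, but a memory benefit acts in the opposite direction.

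**The percentages are assumed.** This stands: 14% is an illustration, not an estimate. Nor does the protocol give reliability data, so poor recall is inferred from the diagnosis, and self-report in the milder MCI subjects may be adequate.

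**Other records exist.** Hospitalizations enter through serious adverse event reporting (9.1, 9.3.2), and concomitant treatments are reviewed throughout. The protocol does not say that either feeds or corrects the HRU endpoint.

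**The partner is imperfect too.** Criterion 6 says should, not must. The partner may be a companion who lives elsewhere or is reached only by phone, and section 9.4 does not say whether partners are blinded. This tells against making the partner the sole source. Joint completion keeps the subject's knowledge and adds the partner's.

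**Driving.** A reader might extend the argument to the driving item because it too is self-rated. Rating one's own ability to drive is a matter of insight rather than recall, and no visit is stated for it, so the calculation does not apply.

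**Conclusion.** The point holds for the HRU endpoint. The protocol chooses the subject as sole stated informant for resource use in a memory-impaired population, while using the caregiver for function and behaviour at all five of the same visits. Under-reporting would dilute a true absolute difference. If treatment improves memory, it would also make the treated arm look costlier: by 6% to 17% for assumed recall of 60% to 90% with a gap of 5 to 10 points, and by 25% for a 15-point gap at 60% sham recall. These sizes depend wholly on recall shares and a look-back period that the protocol does not give.

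A reader might infer that the payor endpoints as a whole rest on an unreliable informant. The documents do not support that: vADAS-Cog, the mobility tests, ADCS-ADL and NPI are performance or caregiver measures. Apart from HRU, only driving and, apparently, the QOL/Patient Survey come from the subject. The primary and secondary efficacy endpoints, and the interim decisions on the primary endpoint, are unaffected. The change is worth making because it is cheap and protects the cost comparison. It does not threaten the trial's main conclusions.

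**What to change.** Amend the RUI entry in section 8.1 so that subject and study partner complete it jointly at the five visits already scheduled, in person or by phone. Use the same informant or informants at each visit, record who answered, and use the joint report for the HRU endpoint in 5.2.3. Keep Appendix C consistent with this, and state the look-back period there if it is not already given. Beside the self-rated driving answer, add a partner rating as a supportive item.

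The cost is a few minutes more in a caregiver contact that already takes place, with no new visit or staff. The remaining weakness is that a partner who does not live with the subject may miss some services; recording the source lets the analyst see where that applies.

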#### Confidentiality Statement

---

The confidential information in this document is provided to you as an investigator or consultant for review by you, your staff, and the applicable Institutional Review Board. Your acceptance of this document constitutes agreement that you will not disclose the information contained herein to others without written authorization from the sponsor.

- **Eligibility Checks and Cognitive Assessments** – Cognitive assessments should be performed as early in the day as possible (before 3:00 PM) and at approximately the same time every assessment. The vADAS-Cog will always be the first assessment performed. Assessments can be performed on the same day as Renew™ NCP-5 treatment as long as they are performed after treatment is completed. If assessments are not performed on the same day as treatment, it is recommended that subjects come in the day following treatment for all assessment testing but no later than 2 days (48 hours) post last Renew™ NCP-5 treatment. Psychometricians/designees will be blinded to treatment.
  - **MMSE2** – The MMSE2 is a brief assessment instrument used to assess cognitive function in geriatric patients. The MMSE2 is used to screen for cognitive impairment and as a measurement of cognitive change over time. It is described in detail in Section 2.
  - **Logical Memory Sub-test of the Wechsler Memory Scale** – is a standardized assessment of narrative episodic memory. A short story is orally presented and the subject is asked to recall the story verbatim (immediate recall). Both Logical Memory I and Memory II will be administered.
  - **MOCA** – The Montreal Cognitive Assessment is a widely used cognitive assessment for patients with Mild Cognitive Impairment due to Alzheimer’s Disease or Mild Dementia of the Alzheimer’s Type. It includes a memory recall test, visuospatial abilities, executive function, attention, concentration, working memory, naming and orientation to time and place.
  - **Cardiovascular Risk Assessment (CVR)** – is a tool to assess the subject’s cardiovascular risk which will be used to stratify subjects at baseline into low/medium risk (< 20% 10 year risk) vs. high/very high risk (>=20% 10 year risk).
  - **Hachinski Scale** – is a tool used to identify a likely vascular component once a dementia diagnosis has been established. Vascular changes more commonly coexist with Alzheimer’s plaques. Scores reflect attention and executive function.
  - **vADAS-Cog** – The vADAS-Cog is made up of ADAS-Cog14 plus three additional tests: the symbol digit test (the number of correct responses in 90 s); the digit span backward test (the number of digits recalled backwards); and the verbal fluency test (animal category in one min). The ADAS-Cog is an instrument devised to assess the severity of cognitive impairment in patients with AD. The scale includes short neuropsychological tests in which the patient performs simple tasks such as word recall, word recognition, and constructional praxis. The cognitive section of the ADAS consists of 11 items, which assess

---

Confidentiality Statement

---

The confidential information in this document is provided to you as an investigator or consultant for review by you, your staff, and the applicable Institutional Review Board. Your acceptance of this document constitutes agreement that you will not disclose the information contained herein to others without written authorization from the sponsor.

the following: language (aphasia), and motor skills (praxis). Rosen, Mohs, et al. (1984) evaluated the test-retest and interrater reliabilities of the individual scale items and the entire scale in patients with dementia of the Alzheimer's type. The ADAS was shown to be valid in the ability to detect patients with clinically diagnosed AD from matched non-demented controls. Because both of the above cognitive and non-cognitive parameters are assessed, the ADAS is a reliable instrument for use in psychopharmacologic trials involving patients with AD.

- **ADCS-CGIC** – assesses clinic global impression of change over time by patient/caregivers and clinicians as indicators of meaningful change and reflects observable changes. Subject should have a caregiver, study partner or companion (which can be a domestic party) and may conduct the assessment over the phone if they do not accompany the participant).
- **ADCS-ADL** – The ADCS-ADL is a set of informant-based items describing performance of activities of daily living assesses the subjects ability to eat, walk, bathe, groom, dress, and other activities of daily living independently by patients with AD. Questions are asked of the caregiver and are given in the form of an interview. Subject should have a caregiver, study partner or companion (which can be a domestic party) and may conduct the assessment over the phone if they do not accompany the participant).
- **Trail Making TEST A & B** – Neuropsychological test of visual attention and task switching that assesses visual search speed, scanning, speed of processing, mental flexibility, and executive functioning. It is the most commonly used test in clinical practice to evaluate patients for MCI or mild AD.
- **2011 NIA-AA criteria** – In 2011, the National Institute on Aging (NIA) at National Institutes of Health (NIH) and the Alzheimer's Association published revised guidelines (NIA-AA) for modernization of the diagnosis of Alzheimer's disease. In these guidelines, the workgroups identified Alzheimer's disease as a continuum with three distinct stages: Preclinical, Mild Cognitive Impairment and Dementia. Checklists to assist in standardizing assessments across sites used to differentiate MCI and dementia will be implemented in this study.
- **Neuropsychiatric Inventory (NPI)** – A behavioral assessment used to assess dementia-related behavioral problems. The NPI is administered to caregivers of dementia patients. Screening questions are used to assess sub-domains of behavioral functioning such as, but not limited to, agitation/aggression, dysphoria, anxiety, irritability/lability, and appetite and eating abnormalities. Positive responses to these screening questions identify problems in the

---

Confidentiality Statement

---

The confidential information in this document is provided to you as an investigator or consultant for review by you, your staff, and the applicable Institutional Review Board. Your acceptance of this document constitutes agreement that you will not disclose the information contained herein to others without written authorization from the sponsor.

associated sub-domain. The caregiver is then asked to rate frequency, severity, and distress of symptoms in the related sub-domain. Higher scores are correlated to patients with dementia.

